## 6.12. Health Outcomes/Quality-of-Life Analyses

### 6.12.1. Patient-Reported Outcomes

The FACT-Leu includes the 27-item cancer-specific Functional Assessment of Cancer Therapy-Leukemia-General (FACT-G) that assesses physical, social/family, emotional and functional well-being plus a 17-item subscale that assesses additional concerns specific to leukemia.

Methods for handling missing data, reverse scoring and other scoring guidelines are provided in [Appendix 1](#).

FACT-Leu results will be summarized descriptively by cycle and for postdiscontinuation visits, including number of completed questionnaires, compliance rates, reasons for noncompliance, scores for each scale, subscale and total scores, and changes from baseline.

Each of the 5 subscales, plus the Leukaemia trial outcome index, FACT-G total score and FACT-Leukaemia total score will be analysed by mixed effect model repeated measures. The model will include randomized treatment, cycle and the interaction of randomized treatment and cycle as fixed effects, with baseline and the interaction of baseline and cycle as a covariate. An unstructured variance covariance matrix will be used, provided data permit. Otherwise the following variance covariance structures will be tested and that with the best fit according to AIC selected: compound symmetry, heterogeneous Toeplitz, first-order autoregressive combined with random patient effect, heterogeneous autoregressive, or heterogeneous compound symmetry. The Kenward-Roger method will be used to estimate denominator degrees of freedom. Least square means and treatment comparisons with corresponding 95% confidence intervals (CIs) for each cycle will be presented in tabular and graphical displays.

### 6.12.2. Resource Utilization

Investigators will be asked to document the use of best supportive care measures, concomitant medications, transfusions, and disease/adverse event-related hospitalization days. Such assessments are to be taken throughout the Phase 2 portion of the study, through the 30-day short-term follow-up, and during the postdiscontinuation follow-up visit.

The proportion of patients receiving concomitant medications for supportive care, and each type of WHO drug name will be summarized by randomized treatment and cycle, including overall cycles, and compared using fishers exact test. Further exploratory analyses may be conducted if warranted, for example the mean number of doses for medications administered to at least 10% of phase 2 patients.

The proportion of patients receiving transfusions will be summarized by randomized treatment and cycle, including overall cycles, and compared between treatment arms using a fishers exact test. Further analyses adjusting for covariates may be conducted if warranted.

The number of hospitalization days, and number of platelet and RBC transfusions, will be summarized descriptively by randomized treatment and cycle.

## 6.13. Bioanalytical and Pharmacokinetic/Pharmacodynamic Methods

The Lilly pharmacokineticist will be responsible for PK and PK/PD analysis.

PK analyses will be conducted on patients who receive at least 1 dose of the study drug and have samples collected. PK parameter estimates for plasma and CSF LY3039478 and plasma dexamethasone, where possible, will be calculated by standard noncompartmental methods of analysis. The primary parameters for analysis will be  $C_{max}$ , area under the plasma concentration-time curve from time zero to last measurable plasma concentration ( $AUC_{[0-t_{last}]}$ ), area under the concentration-time curve from time zero to infinity or over 1 dosing interval at steady state ( $AUC_{[0-\infty]}$  or  $AUC_{\tau}$ ). Other noncompartmental parameters, such as  $t_{1/2}$ , apparent clearance (CL/F), and apparent volume of distribution (V/F) may be reported. Additional exploratory analyses will be performed if warranted by data and other validated PK software programs (for example, NONMEM) may be used if appropriate and approved by Global Pharmacokinetics management. The version of any software used for the analysis will be documented and the program will meet the Lilly requirements of software validation.

The PK data will be combined, and analyses may be conducted to determine a relationship between exposure and PD effect (eg,  $A\beta$ ), data permitting. This model may be used to help reassess the dose cohort escalation as the study progresses. If deemed necessary, PK/PD modeling may be employed to evaluate variability in exposure, pharmacologic effects, and safety parameters.

### 6.13.1. Pharmacodynamics and Tailoring Analyses

Biomarker data from all patients undergoing biomarker assessments will be analyzed using descriptive statistics. Biomarkers (including NICD and gene expression) will be explored at baseline for prognostic value in ORR, EFS or OS outcome, and for potential predictive value in an efficacious response to treatment.

ORR will be summarized by gene mutation status (eg, NOTCH-1/FBXW7/RAS/PTEN) and presented in tabular and graphical displays. Interaction effect between the gene mutation statuses may be further analyzed as warranted.

Further exploratory analyses of pharmacodynamic markers will be conducted as warranted.

## 6.14. Safety Analyses

All safety summaries and analyses will be based upon the safety population that includes patients that have received at least one dose of study drug. Safety analyses will be conducted according to actual treatment received. Data collected for patients receiving LY3039478 plus Dexamethasone following treatment failure of placebo plus dexamethasone included as an additional treatment group in TFLs.

Safety data will be listed and summarized with patient counts and percentages in each treatment arm. Details of the analyses are described in the following sections.

### **6.14.1. Extent of Exposure**

The number of dose omissions, reductions, delays, and cycles received and the dose intensity will be summarized for all treated patients per treatment arm. Summarized data will be provided for the period prior to first CR, the period following first CR, and the total treatment period.

Percent dose intensity is calculated as:

$$100 \times (\text{actual cumulative dose taken (mg)} / \text{planned cumulative dose (mg)})$$

Note that planned dose is the same as actual dose if there is no dose modification or cycle delays. Reasons for dose adjustments will also be summarized, and if the reason for dose modification is due to AE, the associated AE will be provided.

### **6.14.2. Adverse Events**

A listing of all adverse events by patient will be presented. This listing will include patient number, adverse event (actual term and preferred term), event start and end dates, CTCAE grade, relationship to study drug/procedure, seriousness, and outcome. A listing of SAE will be produced using the similar format.

An overall summary will be provided for AEs. The number and percent of evaluable patients will be summarized by treatment for each category below. The summary will provide counts for all AEs, and AEs possibly related to study treatment.

- Patients with at least one TEAE
- Patients with at least one grade 3 or 4 TEAE
- Patients with at least one SAE
- Patients who discontinued due to AE
- Patients who discontinued due to SAE
- Patients who died due to AE on study treatment
- Patients who died due to AE within 30 days of discontinuation from study treatment

**Treatment-emergent adverse events (TEAE)** are defined as follows:

- Any event that first occurred or worsened in severity after baseline, based on the MedDRA LLT term and CTCAE severity grade. This means that any episode of the same AE with the same grade as at baseline that starts after the first dose of study treatment will not be defined as treatment emergent, even if now considered possibly drug related.
- Or any PEC (emerged prior to informed consent) or any AE (emerged after signed informed consent) that were still present prior to first dose but has increased in severity (CTCAE grade) following the start of treatment, regardless of causality.

As per Lilly's standard operating procedures, all "probably related," "possibly related," or "does not know" AEs and SAEs will be defined as related to study drug.

MedDRA v16.1 (or higher) will be used when reporting AEs by MedDRA terms. TEAEs will be summarized by SOC and by decreasing frequency of preferred term (PT) within SOC.

TEAEs will be summarized by CTCAE grade, including the total for maximum Grade 3 and 4, and Grade 3, 4 and 5. These summaries will be provided for events regardless of study drug causality, and repeated for events deemed by the investigator to be possibly related to study medication.

Laboratory parameter abnormalities will be summarized by CTCAE grade.

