10.3.1. Adverse Events

Lilly has standards for reporting AEs that are to be followed regardless of applicable regulatory requirements that may be less stringent. A clinical study AE is any untoward medical event associated with the use of a drug in humans, whether or not it is considered related to that drug.

However, leukemia-related hematologic effects should not be reported as AEs. Because Grade 3 or 4 myelosuppression (leukopenia, neutropenia, thrombocytopenia, and anemia) is expected in

the setting of relapsed T-ALL, these cytopenias will not be considered AEs for the purpose of this study, unless the investigator classifies them as AEs based on clinical circumstances.

Lack of drug effect is not an AE in clinical trials, because the purpose of the clinical trial is to establish drug effect.

Any clinically significant findings from ECGs, laboratory values, vital sign measurements, other procedures, and so on that result in a diagnosis should be reported to Lilly or its designee.

Cases of pregnancy that occur during maternal or paternal exposures to study drug should be reported. Data on fetal outcome and breastfeeding are collected for regulatory reporting and drug safety evaluation.

Study site personnel will record the occurrence and nature of each patient's preexisting conditions, including clinically significant signs and symptoms of the disease under treatment in the study.

After the ICF is signed, site personnel will record the occurrence and nature of any AEs and any change in the preexisting condition(s). All AEs related to protocol procedures are reported to Lilly or its designee.

Investigators will be instructed to report to Lilly or its designee their assessment of the potential relatedness of each AE to protocol procedure and study drug via CRF, electronic data entry or other designated data transmission methods.

Patients will be evaluated for AEs at each visit and will be instructed to call their physician to report any AEs between visits.

The NCI CTCAE v4.0 will serve as the reference document for choosing appropriate terminology for, and grading the severity of, all AEs and other symptoms. For AEs without matching terminology within the NCI CTCAE v 4.0 criteria, the investigator will be responsible for selecting the appropriate system organ class (SOC) and assessing severity grade based on the intensity of the event.

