Overall exposure to study drug, the numbers of patients completing each cycle, and the dose intensity will be summarized using descriptive statistics. The number of patients with any dose adjustment will be presented for entire treatment period as well as for each cycle. The number of patients with dose reductions, dose delays, or dose omissions will also be summarized, as will the reasons for dose adjustments.

An overall summary of AEs will be provided for AEs deemed by the investigator to be possibly related to study medication, and repeated for events regardless of study drug causality. Incidence rates of these events will be compared between treatment arms using Fisher's exact test.

A treatment-emergent AE (TEAE) is defined as an event that first occurred or worsened in severity after baseline.

The number of evaluable patients who experienced a TEAE, SAE, AE related to study drug, died, or discontinued from the study due to an AE will be summarized by treatment.

CTCAE v4.0 (or higher) will be used to report AEs by CTCAE terms.

Laboratory and nonlaboratory CTCAEs will be summarized by CTCAE term and maximum CTCAE grade, including the total for maximum Grade 3 and 4. These summaries will be provided for events regardless of study drug causality, and repeated for events deemed by the investigator to be possibly related to study medication.

MedDRA v16.1 (or higher) will be used when reporting AEs by MedDRA terms. The MedDRA lower level term will be used in the treatment-emergent computation. TEAEs will be summarized by SOC and by decreasing frequency of preferred term (PT) within SOC.

Reasons for death will be summarized separately for on-therapy and within 30 days of last dose of study drug/last visit. Serious adverse events will be summarized by PT.

Hospitalizations and transfusions during the study treatment period or during the 30-day short-term follow-up period will be summarized by treatment group.

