Attachment 1. Protocol I6F-MC-JJCB Study Schedule

Study Schedule, Protocol I6F-MC-JJCB: Phase 1 and Phase 2 Baseline Assessments

	Relative Day Prior to Day 1 of Cycle 1	≤28	≤14	≤7	Notes
Study Entry	Informed consent		X		Informed consent must be signed prior to performing any protocol procedure.
	Inclusion/exclusion evaluation		X		
	Comprehensive medical history			X	
Physical Exam	Physical exam			X	Including testicular exam for males
	Height/weight			X	
	Vital signs			X	Temperature, blood pressure, pulse rate
	Lansky Performance Status			X	For Phase 1 pediatric patients <16 years
	ECOG Performance Status			X	For adults in Phase 1 and Phase 2
Lab and Diagnostic Tests	Electrocardiogram (ECG)			X	Central ECG required
	Echocardiography			X	Echocardiography or another acceptable alternative method to determine ejection fraction such as MUGA scan
	Hematology			X	Manual differentiation
	Serum chemistry			X	Includes: hsCRP, immunoglobins IgA, IgG, IgM
	Coagulation			X	Prothrombin time (PT/INR), partial thromboplastin time (PTT), fibrinogen, d-dimer, antithrombin (AT)
	HTLV			X	
	Urinalysis			X	
	Serum pregnancy test			X	to be performed on women of child-bearing potential
	Archived bone marrow samples			X	For T-ALL patients only. For example, bone marrow biopsies/clot sections/slides >28 days. Lack of sample will not be considered a protocol deviation.
	Archived tumor tissue or tumor biopsy			X	For T-LBL patients only >28 days prior enrollment
	Immunological phenotyping			X	Peripheral blood and bone marrow Lymphocyte panel according Attachment 2
	Expression analysis			X	Peripheral blood
Disease/Tumor Assessment	CT/MRI of head			X	Only if neurological symptoms are present, to detect meningeal disease, chloromas, or CNS symptoms
	CT/MRI thorax and abdomen			X	For T-ALL patients or T-LBL patients followed by CT/MRI
	PET-CT			X	For T-LBL patients with FDG-avid lymphomas
	Lumbar puncture			X	Only if CNS involvement is suspected – see exclusion criterion 20
	Bone marrow biopsy and/or aspirate			X	For T-ALL patients only. With approval from Lilly this sample may be obtained earlier than 14 days.
	Tumor biopsy ^a			X	For T-LBL patients
	CTCAE grading (Preexisting conditions)			X	To be reported only after study eligibility is confirmed
	Concomitant medications			X	
	FACT-Leu			X	Phase 2 Only

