#### **6.14.4. Clinical Laboratory Evaluation**

Listings of all laboratory results will be provided (using SI units [International System of Units], when available) by treatment, for hematology, chemistry, urinalysis, ECG chemistry, immune phenotype, coagulation, CSF and bone marrow. Normal reference ranges, percent of the result outside of range (result divided by lower limit if result is less than lower limit; result divided by higher limit if result is greater than higher limit) and percent change from baseline will also be included. Selected laboratory parameters may be plotted by time.

Laboratory analytes below/above quantifiable levels (data in the database recorded as “ $<x$ ” and “ $>x$ ”) will be reported as such in listings, and imputed to the lower or upper limit of quantification in any summarise or analyses.

Neutrophils, platelets, lymphocytes, monocytes, eosinophils, basophils, RBC, WBC, Nucleated RBCs (NRBC)/100 WBC blasts and other laboratory parameters of interest to disease status will be plotted by time. Data will be log transformed and the logged ratio to baseline analysed by mixed effect model repeated measures with treatment, cycle, and the interaction of treatment and cycle as fixed effects, with baseline and the interaction of baseline and cycle as a covariate. An unstructured variance covariance matrix will be used, data permitting. Otherwise, the following variance covariance structures will be tested and that with the best fit according to AIC selected: compound symmetry, heterogeneous Toeplitz, first-order autoregressive combined with random patient effect, heterogeneous autoregressive, or heterogeneous compound symmetry. The Kenward-Roger method will be used to estimate denominator degrees of freedom. Geometric means and treatment comparisons with corresponding 95% confidence intervals (CIs) for each cycle will be presented in tabular and graphical displays.

A waterfall plot will be provided for minimum percentage bone marrow blasts by treatment arm, coloured by gene mutation status.

A calculated CTCAE grade using CTCAE v4.0 (or higher) will be provided for all laboratory results which can be used independently of clinical judgment to determine a CTCAE severity grade.

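### The laboratory toxicity table by CTCAE grade has no baseline rule, so Grade 4 cytopenia present at entry is mixed with new Grade 4; a shift table would separate them cheaply (minor)

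*SAP*

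**What the plan says.** Protocol 10.3.1 expects Grade 3 or 4 leukopenia, neutropenia, thrombocytopenia and anemia in this disease and rules that "these cytopenias will not be considered AEs for the purpose of this study", unless the investigator decides otherwise in the individual case.

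SAP 6.14.2 defines a treatment-emergent event as one that first appears or worsens after baseline. That rule applies to adverse events. For laboratory data the same section says only: "Laboratory parameter abnormalities will be summarized by CTCAE grade". Protocol 12.2.12 is slightly more specific: "Laboratory and nonlaboratory CTCAEs will be summarized by CTCAE term and maximum CTCAE grade, including the total for maximum Grade 3 and 4". Neither sentence mentions the grade at baseline. SAP 6.14.4 adds that "A calculated CTCAE grade using CTCAE v4.0 (or higher) will be provided for all laboratory results", for those results that can be graded without clinical judgment. The denominator is all treated patients: "All safety summaries and analyses will be based upon the safety population" (SAP 6.14).

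Two other outputs bear on the same question. For platelets, neutrophils and other counts, SAP 6.14.4 states: "Data will be log transformed and the logged ratio to baseline analysed by mixed effect model repeated measures". For transfusions, SAP 6.12.2 states: "The proportion of patients receiving transfusions will be summarized by randomized treatment and cycle", with a Fisher comparison between arms.

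**The concern.** Many patients may already have severe cytopenia at entry. Protocol 9.2.2 treats disease-related marrow suppression as the usual picture, and the organ function criteria in Protocol 7.1 cover liver and kidney only. A patient at Grade 4 at entry who is Grade 4 again on treatment counts in the laboratory table exactly like a patient who falls to Grade 4 on treatment. The table cannot tell the two apart.

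The other grade-based routes do not fill the gap by default. Adverse event tables hold only the cytopenias an investigator reports. The listing of DLT-equivalent toxicities follows a definition that leaves out myelosuppression unless it meets the listed criteria.

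The question is a real one for this drug. Comparing safety between arms is a secondary objective, and Phase 2 is the only placebo-controlled part. Protocol 5.1.6 reports Grade 4 thrombocytopenia as a dose-limiting toxicity in one patient each at 20, 30 and 60 mg, and as possibly drug-related in 3 of 39 patients overall.

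**Working it through.** The plan gives no figure on this point, so there is none to reproduce. The calculation shows what the table measures and how noisy it is.

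**Inputs from the documents.** Arms of 40 and 20 (SAP 5.2). Possibly drug-related Grade 4 thrombocytopenia in 3/39 = 7.7% (Protocol 5.1.6; exact 95% CI 1.6% to 20.9%; no control arm).

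**Assumed inputs, because the documents give none.** b = share of patients at Grade 4 at entry; s = share of those who are Grade 4 again on treatment; p = risk of new Grade 4 among the rest.

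**Formulas, per arm.**
- Planned table: q = b·s + (1−b)·p
- New onset over all treated: r = (1−b)·p
- SD of an arm difference: √[x₁(1−x₁)/40 + x₀(1−x₀)/20], with x = q or r

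**Expected difference.** If s is the same in both arms, b·s cancels and both displays differ by (1−b)(p₁−p₀). With b = 0.5, s = 1, and p = 0.30 v 0.05:
- Planned: 0.5 + 0.5×0.30 = 0.650 v 0.5 + 0.5×0.05 = 0.525; difference 12.5 points
- New onset: 0.150 v 0.025; difference 12.5 points

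If s differs, the two part. With s = 0.8 on LY3039478 and 1 on placebo, the planned table gives 0.40 + 0.15 = 0.550 v 0.525, which is 2.5 points. With the reverse, it gives 0.650 v 0.40 + 0.025 = 0.425, which is 22.5 points. The new-onset difference is 12.5 points in each case.

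**Noise.** With s = 1, the variance of an arm's planned rate exceeds that of its new-onset rate by b(1−b)(1−2p)/n, so noise rises whenever p is below 50%. At b = 0.5:
- Planned: √(0.650×0.350/40 + 0.525×0.475/20) = √(0.00569 + 0.01247) = 0.135
- New onset: √(0.150×0.850/40 + 0.025×0.975/20) = √(0.00319 + 0.00122) = 0.066
- Variance ratio: (0.1347/0.0664)² = 4.1

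**Range over b** (s = 1, new-onset risk 30% v 5%, exact binomial; no excess means the observed rate on LY3039478 is no higher than on placebo):

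| b | Difference, both displays | SD planned | SD new onset, all treated | No excess shown, planned | No excess shown, new onset |
|---|---|---|---|---|---|
| 10% | 22.5 | 11.0 | 8.4 | 3% | 0.7% |
| 30% | 17.5 | 13.2 | 7.6 | 11% | 2% |
| 50% | 12.5 | 13.5 | 6.6 | 20% | 4% |
| 70% | 7.5 | 12.0 | 5.3 | 31% | 11% |

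(Differences and SDs in points.)

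**Incomplete but equal persistence.** With b = 0.5 and s = 0.7 in both arms, the planned table reads 50% v 37.5%, SD 13.4 points, and shows no excess in 20% of trials against 4% for new onset.

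**A smaller effect.** Take an excess of 7.7 points among patients at risk (12.7% v 5%), the size of the documented rate. For b = 10%, 30%, 50%, 70%, no excess is shown in 28%, 37%, 43%, 47% of trials with the planned table and in 20%, 24%, 29%, 37% with new onset over all treated. Two-sided Fisher power at 0.05 in the harmful direction is low either way and lower for new onset: 6.5%, 4.1%, 3.0%, 2.9% against 3.3%, 1.1%, 0.2%, 0.01%.

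**The case against.** The strongest reply is that this is a choice of table and not an error. SAP 6.14.4 already uses baseline for the same analytes: the repeated-measures model takes baseline and its interaction with cycle as covariates and gives treatment comparisons with 95% intervals for each cycle. With 40 and 20 patients, that may answer whether the drug lowers counts better than a dichotomized incidence does. Transfusion use is compared as well, investigators can still report a cytopenia as an adverse event while blinded, the assessment committee sees unblinded safety data, and SAP 6.1 allows extra exploratory analyses. Much of this stands, and it is why the point is minor. What it leaves open is how many patients in each arm newly reached Grade 3/4. A mean ratio to baseline does not give that number, transfusions include patients who were cytopenic on entry, and permission to explore is not a baseline rule set before unblinding.

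A second reply is that Protocol 12.2.12 repeats its graded summaries for events the investigator considers possibly related, which suggests attributed events and not only raw grades. That makes the protocol sentence weaker support. The SAP, however, attaches the repetition by causality to the treatment-emergent summaries and gives the laboratory line on its own.

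A third reply is that every magnitude here is assumed. That is correct. The 30% v 5% case is an excess of 25 points among patients at risk, about three times the documented 7.7%.

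Four stronger readings are tempting and are not supported:
- **That the table's arm difference is biased.** It is a valid randomized contrast for any on-treatment Grade 4. It departs from the new-onset excess only when entry Grade 4 persists unequally.
- **That a planned risk ratio is diluted.** At b = 50% the ratio would read 0.650/0.525 = 1.24 instead of 6, but SAP 6.14 plans counts and percentages, and no risk ratio for laboratory grades.
- **That cytopenia is analysed without any baseline adjustment.** The model in SAP 6.14.4 contradicts this.
- **That separating new onset would gain power.** With the smaller effect it loses power at every b examined.

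**Conclusion.** The point holds as a cheap improvement, severity minor. Followed as written, the one default grade-based display of cytopenia mixes what patients brought with them and what happened on treatment. Its difference can be read as new-onset excess over all treated patients only under equal persistence of entry Grade 4. Persistence of 80% v 100%, at 50% Grade 4 at entry, would turn an excess of 12.5 points into 2.5. Even with equal persistence the table is noisier for new onset: 13.5 against 6.6 points in the same scenario.

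These sizes rest on assumed entry shares, persistence and new-onset risks. The direction of the noise result needs new-onset risk below 50% among patients at risk when entry Grade 4 always persists. The unbiasedness statement covers the randomized arms only, not the group that crosses over from placebo. One descriptive table is affected; no hypothesis test or stopping rule depends on it.

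**What to change.** Keep the planned grade table. In SAP 6.14.2 and 6.14.4, for platelets, neutrophils and hemoglobin where the grade follows from the result alone, add by arm:

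1. A shift table of baseline grade by worst on-treatment grade.
2. The incidence, with exact 95% CI, of worsening to Grade 3/4 and to Grade 4, both among patients below that grade at baseline and over all treated patients, with platelet transfusions flagged.

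Label both as descriptive and present them beside the repeated-measures model and the transfusion summaries.

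Baseline hematology (Protocol Attachment 1), calculated grades (SAP 6.14.4) and transfusion data (SAP 6.12.2) are already planned. The cost is SAP wording and standard table programming, with no new visit, sample or test. The drawback is small at-risk denominators: about 20 v 10 if half are Grade 4 at entry, where 6/20 v 1/10 would give intervals of 11.9% to 54.3% and 0.3% to 44.5%. There is no power gain when the excess is small. New-onset counts also miss prolongation of cytopenia already present, which is why the planned table and the shift table both stay.
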